## 2.4 Number of Subjects / Study Sites

It is planned to assign 756 patients at 20–30 trial sites within a recruitment period of 48 months, which results in about 8 recruited patients per center per year.

The study is event-driven, at least 45 primary endpoint events need to be observed to demonstrate the non-inferiority of laparoscopic or robot-assisted radical/simple hysterectomy compared to abdominal radical/simple hysterectomy with regard to disease-free survival (DFS) using a pre-defined non-inferiority margin of 2.3 for the hazard ratio (HR).

## 2.5 Study Duration

Study duration is defined as the time from First-Patient-In (FPI) to Last-Patient-Out (LPO). The total duration of the trial will be 108 months (nine years) including a recruitment period of 48 months (4 years).

Study duration per patient will take a minimum of 60 months (5 years). The duration of the surgical intervention per participant depends on individual circumstances and will take between 150 and 300 minutes followed by a follow-up period of at least 60 months (5 years).

The study is event-driven and can be terminated after 45 primary endpoint events have been observed. In addition to that the trial steering committee in cooperation with the DMC may terminate enrolment at any time if this seems to be in the best interest of the patients.

### 2.6 Randomization

A permuted block randomization with randomly selected block sizes will be conducted to allocate patients to both treatment arms in a 1:1 ratio. The randomization will be stratified by the following factors:

- tumor size (<2cm vs 2-<4 cm)
- sentinel node mapping only (Yes vs No)
- radical vs simple hysterectomy (SHAPE criteria)
- anticipated type of minimally invasive surgery (laparoscopic vs robot-assisted)
- center

Treating physicians will determine the type of minimally invasive surgery (laparoscopic or robot-assisted) upfront randomization to enable stratification. The type of laparoscopic surgery, whether conventional or robotic, is determined by the surgeon based on the surgeon's experience and preference. If a simple hysterectomy is to be considered for patients with low-risk early-stage cervical cancer meeting the SHAPE-criteria (tumor < 2cm, < 10 mm depth of stromal invasion (LEEP/cone) this must already be determined before the randomization process.

Randomization will only be performed after verification of the patient's eligibility and signed written informed consent. All inclusion criteria and no exclusion criteria must be met. Furthermore, baseline assessment of quality of life questionnaires will be performed prior to randomization.

Patients will be randomized using the electronic randomization tool provided within the eCRF/electronic data capture (EDC) system.

## 2.7 Protocol Deviations (PD)

All PDs will be tracked and actions will be defined, as feasible. All PDs classified as major will be reviewed in Data Review Meetings by the TSC for the final analysis for assessment of their influence on the quality of the study analysis.

Protocol deviations (PD) are defined as follows:

Major PD:

- Informed consent procedure: ICF not signed and dated by subject/investigator
- Violation of an in- or exclusion criterion
- Deviations affecting the primary endpoint of the study
- Absence of source data in the patient's medical records/absence of the patient file
- Non-compliance with the protocol and protocol amendments (e.g. study visits not in accordance with protocol
- Missing or delayed reporting of serious adverse events (SAE)

## 2.8 Premature Discontinuation of the Study

The responsible investigator can decide to terminate the trial at his/her study site at any time for reasonable medical or administrative reasons. Stopping rules for individual patients are listed in section 3.4. A DMC will evaluate the trial and the obtained data in the context of safety, validity and quality on a regular basis and can recommend early termination (see section 9.2). If the study is prematurely terminated for any reason, the investigator has to ensure appropriate therapy and follow-up of subjects included in the clinical trial.

### **3 STUDY POPULATION**

## 3.1 Study Population/Condition

For this trial female patients, aged 18 years or older, with operable early-stage cervical cancer FIGO stage IA2 to IB2 (< 4 cm tumor size) and a histologic subtype of squamous-cell carcinoma, adenocarcinoma, or adenosquamous carcinoma can be recruited. In Germany there are about 4500 cervical cancer cases per year with a percentage of 60% stage I cervical cancer diagnoses.

According to sample size calculation it is necessary to include at least 286 women with early-stage cervical cancer per treatment arm in order to determine the minimally invasive surgery's non-inferiority compared to ARH. For more relevance of the results we plan to recruit 378 patients per arm. Therefore, it is planned to assign 756 patients at 20–30 trial sites within a recruitment period of 48 months, which results in about 8 recruited patients per center per year. It is estimated that 2100 women need to be assessed for eligibility to achieve full patient recruitment.

Participants will be primarily recruited from the centers' patient pools. After obtaining oral and written informed consent all women who undergo screening will be documented in a screening and enrollment log. Patients who sign an informed consent form but do not meet eligibility criteria are defined as screening failures. Eligible patients meeting all inclusion and no exclusion criteria will be randomly allocated to one of both treatment arms. A subject-ID will be assigned which will also be documented in the screening and enrollment log. It is composed of two digits for the site and 3 digits for the sequential number of the patient in the site, e.g. 02-004.

Additionally, it is planned to collect biomaterials at different time-points during the course of the trial. This includes urine samples and pap smear (thin prep) from the cervix either at visit 2 or visit 3 as well as blood samples and tumor material at visit 3. Biomaterials will be labeled with the subject ID as well. The following abbreviations will be used: B = blood sample, T = tumor material, L = lymph node material, P = pap smear from cervix (thin prep), U = urine. The final label will be composed as follows: **CENTER** (\_\_) **\_ Randomization Number** (\_ \_ ) **\_ BIO \_ Visit No**. **\_ Material** (**T = Tumor/B = Blood/L = Lymph/P = Pap Smear/U = Urine**)

e.g. 01\_001\_BIO\_1\_T, indicating a probe from: center 1, randomized patient 1, drawn at visit 1, Tumor Material. Furthermore, registration data has to be entered to an electronic Case Report Form (eCRF).

These biomaterials will then be used to enable accompanying scientific projects related to the treatment of cervical cancer in the future. Biomaterials will only be collected if the patient agrees to these procedures and signs a separate consent for the collection of biomaterials.

## 3.2 Inclusion Criteria

Patients eligible for inclusion in this study have to meet all of the following criteria:

- 1. Histologically confirmed primary adenocarcinoma, squamous cell carcinoma or adenosquamous carcinoma of the uterine cervix
- 2. Patients with FIGO stage IA2, IB1 or IB2 disease (< 4 cm)
- 3. Patients undergoing radical hysterectomy according either to Type II or III (Piver Classification) or to Type B or C (Querleu and Morrow classification)

OR

Simple hysterectomy can be considered for patients with low-risk early-stage cervical cancer (SHAPE criteria:

tumor < 2cm, < 10 mm depth of stromal invasion (LEEP/cone). Simple hysterectomy has to be performed as extrafascial hysterectomy and the preparation of a max. 5mm vaginal cuff is required to ensure negative margins.

- 4. Performance status of ECOG 0-1
- 5. Patient must be suitable candidates for surgery for instance with preoperative MRI and available for assessment of serious adverse events up to 3 or 6 months post-surgery
- 6. Patients who have signed an approved Informed Consent
- 7. Patients with a prior malignancy only if > 5 years previous with no evidence of disease
- 8. Females aged 18 years or older

### 3.3 Exclusion Criteria

Patients eligible for inclusion in this study must not meet any of the following criteria:

- 1. Any histology other than an adenocarcinoma, squamous cell carcinoma or adenosquamous carcinoma of the uterine cervix
- 2. Tumor size 4 cm and greater, estimated by either magnetic resonance imaging (MRI) or clinical examination
- 3. FIGO stage IB3 IV
- 4. Patients with a history of pelvic or abdominal radiotherapy
- 5. Patients with evidence of metastatic disease by conventional imaging studies, enlarged pelvic or aortic lymph nodes > 2 cm, or histologically positive lymph nodes
- 6. Serious concomitant systemic disorders incompatible with the study (at the discretion of the investigator)
- 7. Patients unable to withstand prolonged lithotomy and steep Trendelenburg position
- 8. Patient compliance and geographic proximity that do not allow adequate follow-up
- 9. Women who are pregnant
- 10. Patients with contraindications to surgery
- 11. Patients with secondary invasive neoplasm in the last 5 years (except non-melanoma skin cancer, breast cancer T1 N0 M0 grade 1 or 2 without any signs of recurrence or activity)

### **3.4** Premature Subject Discontinuation (Drop-Out)

Participation in the clinical trial is voluntary. Subjects have the right to withdraw consent and discontinue participation in the study at any time for any reason and without prejudice to further treatment. Subjects are not obliged to state a reason for discontinuation but investigators are asked to try to identify the reason. During the initial informed consent procedure subjects will be asked for their consent to be contacted for a final examination irrespective of whether they have discontinued their study participation prematurely or not.

The investigator has the right to withdraw a subject from the study if the subject's safety or wellbeing is compromised or if the subject is not compliant. Subjects who discontinue the treatment for any reason will remain in the study to be evaluated for efficacy and safety endpoints and will be expected to continue study visits.

Concern for the interests of the subject must always prevail over the investigator's/study interests. The investigator must ensure appropriate treatment of the subject after withdrawal.

Whenever possible, investigators should discuss discontinuation of an individual subject with the responsible investigator in advance.

Medical circumstances that may lead to exclusion of the subject include but are not restricted to:

- Occurrence of AEs or SAEs which preclude study treatment or further study participation
- Occurrence of any of the predefined exclusion criteria
- Significant protocol violation including non-compliance with study assessment
- Subject requests to discontinue for any reason; it is important to determine whether the request is primarily due to an SAE, lack of efficacy or other reason.

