#### Experimental Treatment

In the standard arm, radical hysterectomy is performed as per standard technique (abdominal radical hysterectomy (Piver type 2 or 3 or Querleu & Morrow Type B or C) with salpingectomy +/- oophorectomy. Ovaries may be removed or preserved +/- transposition. Surgery includes pelvic lymph node dissection or optional sentinel lymph node biopsy (SNB) according to current guidelines in both study arms.

In the experimental arm, radical hysterectomy is performed as per standard conventional 2D/3D laparoscopic or robotic assisted technique (Querleu & Morrow Type B or C) with salpingectomy +/- oophorectomy. Ovaries may be removed or preserved +/- transposition. The following protective measures are mandatory for the minimal-invasive arm: LEEP/conization before randomization or closure of the vagina before colpotomy. Transcervical manipulators are not permitted. Use of uterus manipulators/ cervical adapter (without transcervical device) are allowed only after LEEP/conization. Meticulous dissection of pelvic (sentinel) lymph nodes including use of endobags and avoiding the dissemination of cancer cells will be implemented (tumor hygiene).

Due to the positive results of the SHAPE trial presented at ASCO 2023, in both arms simple hysterectomy can be considered for patients with low-risk early-stage cervical cancer (SHAPE-criteria: tumor < 2cm, < 10 mm depth of stromal invasion (LEEP/cone) BUT has to be determined BEFORE randomization. Surgery can be performed including removal of the sentinel lymph nodes following the concept of sentinel lymph node biopsy (SNB) and according to the current guidelines. Simple hysterectomy has to be performed as extrafascial hysterectomy and the preparation of a max. 5mm vaginal cuff is required to ensure negative margins.

The Follow-Up period begins 1 month (+/- 7 days) after surgical treatment and will take a minimum of 5 years per patient.

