## 7.1.2 Primary endpoint

The primary endpoint disease-free survival (DFS) will be analyzed according to the intention-to-treat (ITT) principle which includes all patients as randomized. The DFS curves will be estimated using the Kaplan-Meier method. A Cox proportional hazards model adjusted for the stratification factors for the randomization will be used for the comparison of minimally invasive and open surgery. Non-inferiority of minimally invasive as compared to open surgery will be declared if the upper boundary of the two-sided 95% CI for the hazard ratio (minimally invasive / open) is below the predefined non-inferiority margin of 2.3. A sensitivity analysis will be performed according to the per-protocol (PP) principle which includes all randomized patients where surgery has been performed according to the initial randomization. Consistency between results in the ITT and PP analysis is needed to draw meaningful conclusion regarding differences in DFS.

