Sample size estimation for the G-LACC trial was performed in nQuery Advisor version 9 using the non-inferiority test for two survival curves using Cox regression. The one-sided type I error is set to 2.5% and the aimed power is set to 80%. With an assumed probability of primary endpoint event of 6% (=1-94%) at 4.5 years in both arms and each patient will be followed-up for about 4.5 years, a sample size of 378 patients per arm (756 patients in total) will be required to observe 45 primary endpoint events to declare the non-inferiority of minimally invasive surgery compared to open surgery with a non-inferiority margin of 2.3 for the hazard ratio for DFS. The study is event-driven and can be terminated after 45 primary endpoint events have been observed.

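### Section 3.4 lets the investigator withdraw a randomised woman from the study for non-compliance or a protocol violation, without securing her later DFS and OS follow-up

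*Protocol*

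**What the plan says.** Protocol section 3.4 contains four relevant provisions.

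- The investigator may "withdraw a subject from the study if the subject's safety or wellbeing is compromised or if the subject is not compliant".
- An open-ended list of circumstances that may lead to exclusion includes "Significant protocol violation including non-compliance with study assessment".
- The sentence right after the investigator's right reads: "Subjects who discontinue the treatment for any reason will remain in the study to be evaluated for efficacy and safety endpoints".
- At the initial consent, women are "asked for their consent to be contacted for a final examination irrespective of whether they have discontinued their study participation prematurely or not".

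Section 2.8 refers to 3.4 for the stopping rules for individual patients, so this text is operative.

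Three other sections bear on it.

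- Section 2.7 classes non-compliance with the protocol, with off-schedule visits as its example, as a major deviation. Major deviations are reviewed by the steering committee for the final analysis. Removal is not mentioned.
- Section 7.1.2 bases the primary DFS analysis on an ITT set that "includes all patients as randomized". The per-protocol set keeps every woman operated on as allocated.
- Section 4.1 (Experimental Treatment) states: "The following protective measures are mandatory for the minimal-invasive arm". These are prior conization or vaginal closure before colpotomy, together with limits on manipulators.

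**The concern.** An ITT analysis protects the comparison only if outcomes are still observed in the women it includes. Treatment here is a single operation, so a woman who becomes non-compliant afterwards has no treatment left to discontinue. The retention sentence therefore does not clearly reach her, while the right to withdraw her from the study does. Follow-up is meant to last at least five years, and 3.4 secures one final examination.

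The person who decides knows the arm and the course of the operation. The form in 5.3.4 records manipulator type and vaginal closure, with none as an option. If removal is related to prognosis, censoring is informative. If it also differs between arms, the hazard ratio is biased. In a non-inferiority trial, loss of high-risk women from the experimental arm pushes towards a false positive conclusion.

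**Working it through.** **1. Provisions side by side**

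| Situation | Section 3.4 | Elsewhere |
|---|---|---|
| Treatment discontinued | Stays in for efficacy and safety | Consistent with 7.1.2 |
| Visits or assessments missed | Ground for withdrawal or exclusion | 2.7: major deviation, reviewed for the analysis |
| Other significant protocol violation | Ground for exclusion | 2.7: deviation; 7.1.2: kept in ITT, and in PP if operated on as allocated |
| After leaving the study | Consent to a final examination | Follow-up of at least 5 years (2.5, 4.2) |

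Neither analysis set in 7.1.2 needs these removals, and 2.7 already has a route for the same conduct.

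**2. The plan's event count**

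Inputs from 7.2: one-sided 2.5%, power 80%, margin 2.3, true HR 1, 1:1 allocation, and "With an assumed probability of primary endpoint event of 6% (=1-94%) at 4.5 years in both arms".

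- Events = 4 × (1.960 + 0.842)² / (ln 2.3)² = 45.26. The plan's 45 is reproduced.
- Patients = 45.26 / 0.06 = 754.3, so 378 per arm or 756 in total.
- 756 × 0.06 = 45.4, so the sample size contains no allowance for loss at 4.5 years.

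**3. Does random loss cost power?**

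Hazard = −ln(0.94)/4.5 = 0.01375 per year. With the five-year minimum follow-up, 756 × (1 − exp(−0.01375 × 5)) = 50.2 events are expected. With 10% lost at once, 0.90 × 50.2 = 45.2 remain. The trial is event-driven, so 45 events stay within reach and no power loss follows.

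**4. Selective censoring, a hypothetical illustration**

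Assumptions:

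- A share v of the minimally invasive arm is removed right after surgery.
- These women have r times the hazard of the other women in that arm.
- Nobody is removed from the open arm.
- The true all-randomised HR equals the margin.

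The observed HR is h = 2.3 / (1 − v + v·r). With 45 events, SE(log HR) ≈ 2/√45 = 0.298. False non-inferiority = 1 − Φ(1.96 − ln(1 − v + v·r)/0.298).

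The range for r comes from a retrospective European cohort described in section 1.4 (4.5-year DFS). Without versus with cuff closure: ln 0.74 / ln 0.93 = 4.15. With versus without a manipulator: ln 0.73 / ln 0.83 = 1.69.

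| v | r | 1 − v + v·r | Observed HR | False non-inferiority |
|---|---|---|---|---|
| any | 1 | 1 | 2.30 | 2.5% |
| 5% | 1.69 | 1.034 | 2.22 | 3.2% |
| 5% | 4.15 | 1.157 | 1.99 | 7.1% |
| 10% | 1.69 | 1.069 | 2.15 | 4.1% |
| 10% | 4.15 | 1.315 | 1.75 | 14.9% |

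A second calculation takes r as 2 or 3 and uses arm-specific events at 4.5 years, with SE = √(1/d_open + 1/d_min). Here d_open = 378 × 0.06 = 22.7 and d_min = 378(1 − v)(1 − exp(−h × 0.01375 × 4.5)). It gives 3.8% and 5.6% for v = 5%, and 5.5% and 10.2% for v = 10%.

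**The case against.** A reader might infer that 3.4 directs the removal of women whose minimally invasive operation broke the containment rules, so that a bias towards non-inferiority is built in. The text does not say that. The investigator's right concerns the woman's own compliance. The list is introduced as medical circumstances, and its one example of a significant violation is missed assessments. Surgical quality is handled elsewhere: through deviations (2.7) and at centre and surgeon level (9.3.3, 9.5). Missed assessments can occur in both arms, and so can breaches of the rules on type of hysterectomy, vaginal cuff or sentinel nodes. The open wording does not exclude containment breaches, but one-sided removal remains an inference.

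Withdrawal is also discretionary and, where possible, is to be discussed beforehand with the responsible investigator. Events can be lost; the documents do not show that they will be. Nor does 3.4 flatly contradict ITT: a withdrawn woman can stay in the analysis set, censored at her last contact. The weakness is in what is observed, not in who is counted.

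The illustration is open to challenge too. The removal shares are assumed, and women who miss visits would leave later than the calculation supposes. The ratio of 4.15 is a crude retrospective contrast, and section 1.4 itself warns of selection bias in such data. It compares closure with no closure, whereas this protocol allows no closure after conization. The 14.9% is therefore a corner case.

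Finally, a reader might infer lost power from the missing loss allowance. Step 3 shows why this does not follow.

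What the objection leaves standing is the gap: two discretionary triggers can end endpoint follow-up, and nothing in 3.4 says that it continues.

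**Conclusion.** The point holds as a defect of wording with a possible effect on bias. An investigator who follows 3.4 as written may end the follow-up of a randomised, operated woman for conduct that 2.7 treats as a deviation to be recorded. Only a final examination is then provided for. In an open-label non-inferiority trial analysed by ITT, this permits informative censoring of the primary endpoint.

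The size cannot be derived from the protocol. If 5% of the minimally invasive arm alone were removed early, with 1.7 to 4.1 times the hazard of the others, false non-inferiority at a true HR of 2.3 would be about 3% to 7% instead of 2.5%. With equal hazards it stays at 2.5%, and removals from the open arm could offset or reverse the effect. No power loss is claimed. The change is worth making because it is cheap and removes the question from the interpretation of the result.

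**What to change.** In section 3.4:

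- Delete non-compliance as a ground for withdrawal from the study.
- Delete the bullet on significant protocol violation.
- State that non-compliance and protocol deviations, including surgery without the mandated measures, are recorded under 2.7 and do not end DFS and OS follow-up.

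In the consent form, in addition to the final examination, ask for agreement that recurrence and vital status may still be collected after visits stop, from records, the treating physician or registers, as national rules allow.

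Leave the safety or wellbeing ground and the AE/SAE ground as they are; this point does not concern them.

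Cost: a protocol amendment and an updated consent form. Women already enrolled would be asked to sign the new form (10.3), and sites outside Germany may face different rules on register data. Physician or registry enquiries take a small effort. No extra patients are needed.

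### Section 3.4 lets a randomised woman be excluded when an exclusion criterion is met after randomisation, which conflicts with the retention sentence in the same section and with the ITT analysis in 7.1.2

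*Protocol*

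**What the plan says.** Section 3.4 (Premature Subject Discontinuation) ends with a list of medical circumstances that may lead to exclusion of the subject. One bullet reads "Occurrence of any of the predefined exclusion criteria". It is not limited to the period before randomisation or before surgery. Section 2.8 refers to 3.4 as the place where stopping rules for individual patients are found.

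Exclusion criterion 5 in section 3.3 is: "Patients with evidence of metastatic disease by conventional imaging studies, enlarged pelvic or aortic lymph nodes > 2 cm, or histologically positive lymph nodes". Criterion 3 covers FIGO IB3 to IV. Criterion 2 covers tumours of 4 cm or more, as estimated by MRI or clinical examination.

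Two other passages point the other way. Section 3.4 also states: "Subjects who discontinue the treatment for any reason will remain in the study to be evaluated for efficacy and safety endpoints". Section 7.1.2 analyses DFS by the "intention-to-treat (ITT) principle which includes all patients as randomized".

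**The concern.** Randomisation takes place at visit 2 and surgery at visit 3 (5.1). Under 4.1 and 4.1.2, nodal histology comes from frozen section and later ultrastaging of tissue removed at surgery. The examination under anaesthesia that verifies clinical stage (4.1.1) is also at surgery. Positive nodes and a higher stage can therefore first become known in women who are already randomised. They are also prognostic: section 1.2 gives 5-year overall survival below 75% with nodal metastasis, against 90% for early-stage disease without lymphatic spread.

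If a site applied the bullet to such a woman, her follow-up could end. ITT would still count her as randomised, but she would be censored at a moment linked to her risk, and any later recurrence or death would be missing from the primary analysis. The trial is open-label (2.1), so the arm is known when the decision is made. A later analysis plan cannot restore follow-up that was never collected.

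**Working it through.** **1. The passages side by side**

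- *Can the bullet mean a check before randomisation?* Hardly. Women who fail eligibility at screening are already defined as screening failures (3.1, 5.2.1), and breaches of an eligibility criterion are already major protocol deviations (2.7). The bullet sits in the drop-out section and speaks of occurrence.
- *Which criteria can be newly met at surgery?* Positive nodes (criterion 5) and a revised stage (criterion 3). Criterion 2 could at most be met at the examination under anaesthesia.
- *Does the retention sentence cover these women?* Only in part. It concerns those who discontinue the treatment, and treatment here is one operation. A woman whose hysterectomy is abandoned for lymphatic spread (4.1) falls under both sentences of 3.4, which then disagree. A woman whose operation is completed and whose final histology shows a positive node has discontinued nothing, so the retention sentence does not reach her.
- *Does ITT cure it?* It fixes who is analysed. It does not supply events after follow-up ends.

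**2. The planned figure reproduced**

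Inputs from 7.2: one-sided alpha 2.5%, power 80%, margin 2.3, 6% event probability at 4.5 years in both arms (so true HR 1). Allocation is 1:1 (2.1). The plan states: "a sample size of 378 patients per arm (756 patients in total) will be required to observe 45 primary endpoint events".

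- Events = (1.960 + 0.842)² / (0.25 × ln(2.3)²) = 45.26
- Women = 45.26 / 0.06 = 754.3, or 377.1 and so 378 per arm
- Expected events = 756 × 0.06 = 45.4

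The stated 45 events and 378 per arm reproduce. Section 7.2 states no allowance for dropout.

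**3. Events lost equally in both arms and not replaced**

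Power = Φ(ln(2.3) × √D / 2 − 1.960). The number lost is an assumption.

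| Events lost | D | Power |
|---|---|---|
| 0 | 45 | 79.8% |
| 2 | 43 | 78.0% |
| 4 | 41 | 76.0% |
| 6 | 39 | 73.9% |
| 9 | 36 | 70.5% |

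**4. Events lost only in the minimally invasive arm**

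Suppose the true HR is 2.3, 45 events are analysed, and a share f of the events in that arm is never observed. The apparent HR is 2.3 × (1 − f), and the true one-sided error is Φ(−ln(1 − f) / (2/√45) − 1.960).

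| f (assumed) | Apparent HR | One-sided error (nominal 2.5%) |
|---|---|---|
| 5% | 2.18 | 3.7% |
| 10% | 2.07 | 5.4% |
| 15% | 1.95 | 7.9% |
| 20% | 1.84 | 11.3% |

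**5. How sensitive one result would be**

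With equal arms and the HR approximated by the ratio of events a/b, the upper 95% limit is (a/b) × exp(1.96 × √(1/a + 1/b)).

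| Events, minimally invasive vs open | HR | Upper limit | Against 2.3 |
|---|---|---|---|
| 27 vs 18 | 1.50 | 2.72 | fails |
| 23 vs 18 (4 lost in one arm) | 1.28 | 2.37 | fails |
| 22 vs 18 (5 lost in one arm) | 1.22 | 2.28 | passes |
| 22 vs 17 (5 and 1 lost) | 1.29 | 2.44 | fails |
| 24 vs 16 (one ninth lost in each arm) | 1.50 | 2.82 | fails |

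In this example the conclusion changes only with a one-sided loss of 5 events. Proportional loss makes non-inferiority harder to show.

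**The case against.** The case against is substantial. The list is permissive, and 3.4 asks that discontinuation be discussed beforehand with the responsible investigator whenever possible. The rest of the protocol expects node-positive women to stay. Section 5.3.9 records positive node counts and final TNM, 5.3.10 and the study calendar record adjuvant treatment at one year, and 2.7 treats a violated eligibility criterion as a deviation for review. The sentinel procedure is the same in both arms (4.1.2), so positive nodes give no reason in themselves to expect different loss by arm. All of this stands. It makes misuse less likely, but the bullet still says what it says.

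A reader might infer more, in four ways that the documents do not support:

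- *That a final pathological size of 4 cm or more triggers exclusion.* Criterion 2 is limited to MRI or clinical examination.
- *That metastases seen on follow-up imaging allow a woman to be dropped before her recurrence is dated.* Sections 2.3.2 and 5.3.14 govern suspected recurrence: it must be verified by histopathology and is dated at biopsy. Letting a general drop-out bullet override that procedure is a strained reading.
- *That the hazard ratio will be biased towards non-inferiority.* That needs unequal loss. It is possible in an open-label trial, but nothing in the protocol shows it.
- *That the number of events at risk can be stated.* The documents give neither the node-positive share nor its DFS event risk. Assuming shares of 5% to 15% and risks of 20% to 30% gives from 756 × 0.05 × 0.20 = 7.6 to 756 × 0.15 × 0.30 = 34.0 events. A range that wide measures the assumptions, and it counts women who may be excluded, not women who would be.

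**Conclusion.** The point holds as an unreconciled contradiction. Section 3.4 permits follow-up of a randomised woman to end because of a finding first made at surgery that marks higher risk. Another sentence of 3.4 and the ITT principle in 7.1.2 require the opposite. It is not an instruction to remove these women from the analysis set.

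The likely cost under equal proportional loss is power: 76.0% if 4 of 45 events are lost, assuming that they are not replaced by longer follow-up. The trial is event-driven, so some replacement may be possible. If loss fell only on the minimally invasive arm and took 10% of its events, the one-sided error at the margin would rise from 2.5% to about 5.4%. That is a conditional calculation, not a forecast.

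**What to change.** Reconcile 3.4 with 7.1.2:

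- Delete the bullet, or limit it to eligibility judged on information available before randomisation.
- Add one sentence: women found after randomisation to meet an exclusion criterion (for example positive nodes, upstaging or suspected metastatic disease) stay in DFS and OS follow-up unless they withdraw consent to follow-up.

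This concerns follow-up only. It implies no change to treatment and leaves the investigator's right to withdraw a subject for safety or non-compliance as it is. The sample size and event target are unchanged. The cost is one paragraph in a protocol amendment and a notice to sites. It should be made while the trial is running, because missed follow-up cannot be recovered at analysis.
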